#### 8.1.2 Secondary study parameters/endpoints

The secondary objectives of this study are to assess the following secondary endpoints:-

The key secondary objective is:

- Treatment failure defined as an incomplete resolution of the clinical signs and symptoms associated with the AECOPD at day 30 after inclusion of the study (i.e not reaching the baseline condition prior to the AECOPD) scored using the modified Anthonisen criteria.

The other secondary objectives are:

- Change in Quality of Life on day 1, 10, and after 30 days using the COPD Assessment Test (CAT)
- Decision to start antibiotic therapy after an initial opposite decision (after 48 hours)
- Side effects (gastro-intestinal complaints, allergic reactions)
- Cumulative antibiotic consumption
- Cumulative prednisolone consumption
- Length of hospitalization
- Time to complete resolution of symptoms according to daily symptom diaries evaluating the modified Anthonisen criteria
- Re-exacerbation within 30 days
- PROM symptom score: EXACT – Respiratory symptoms scale (at admission, at day 10 and at day 30 after admission)
- Non-Invasive ventilation after 72 hours of admission

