**8.3 Study procedures**

**Study period:**

All the assessments will be done at baseline, at day 10 and day 30.

Patients diary cards will be reviewed at each visit for symptoms and exacerbations

	Day 1	Day 3	Day 5	Day 10	Day 30
Initiation procedures					
Informed consent	X				
Medication history	X				
Vital signs	X				
Check for eligibility	X				
Sputum collection	X				
Blood sampling, including procalcitonin*	X				
Blood sampling CRP, eosinophils	x				
Serum for storage	X				
Sputum for storage	X				
Modified Anthonisen criteria	X	X	X	X	X
Clinical assessment for treatment failure		X	X	X	X
CAT	X			X	X
E-RS	X			X	X
EQ-5D-5L	X			X	X
iMCQ					X
Randomization	X				

Antibiotic consumption	X	X	X	X	X
Diary cards according to modified Anthonisen criteria**	X	X	X	X	X
Assessment of adverse effects	x	X	X	X	X

\* (PCT will only be reported for the randomised PCT group and not for the usual care group during the study period. The measurement will be performed in the usual care group but this will be blinded until the study ends.)

\*\* This symptom card will be evaluated on the given days by the patient

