6.4 Study Assessments

Visit	Baseline	Day 3	Day 5	Day 10	Day 30
Informed consent	x				
Medication history	x				
Vital signs	x				
Check for eligibility	x				
Sputum collection	x				
Blood sampling, including procalcitonin*	x				
Blood samples for CRP, eosinophils	x	x	x		
Serum for storage	x				
Sputum for storage	x				
Modified Anthonisen criteria	x	x	x	x	x
Clinical assessment for treatment failure		x	x	x	x
CAT	x			x	x
EXACT-RS	x			x	x
EQ-5D-5L + resp. bolt-on	x			x	x
iMCQ (adapted version)					x
Randomization	x				
Antibiotic consumption	x	x	x	x	x
Prednisolone consumption	x	x	x	x	x
Diary cards according to modified	x	x	x	x	x

Anthonisen criteria					
Assesment of adverse effects/events	x	x	x	x	x

* (PCT will only be reported for the randomised PCT group and not for the usual care group during the study period. The measurement will be performed in the usual care group but this will be blinded until the study ends.)

Analysis Time Windows

Visit (target day)	Lower bound (days)	Upper bound (days)
Baseline (0)	N/A	N/A
Day 3	N/A	N/A
Day 5	N/A	N/A
Day 10	9	11
Day 30	28	32

This section will go beyond the description of variables provided in the protocol in that it will list and describe all important study variables from a statistical perspective. The description of each variable should include:

- Modified Anthonisen criteria
 - Items are measured on with 3 optional answers where the first option = no deterioration, the second is slightly worse and the third option = much worse.
- EXACT respiratory symptoms questionnaire
 - Comprised of 11 questions about respiratory symptoms common for patients with COPD
 - Items are measured on a 0-3 or 0-4 ordered categorical scale for which a 0 = not at all, 1 = slightly or rarely or a little (depending on the question), 2 =moderately, 3 = severely or quite a bit, and 4 = extremely
 - The answer scales slightly differ depending on the question, for example breathlessness is scored on 0-3 ordered categorical scale for which a 0 = unaware of breathlessness, 1 = breathless during strenuous activity, 2= breathless during light activity, 3= breathless when washing or dressing, or present when resting
- COPD assessment test (CAT)
 - Comprised of 8 items to assess the impact of COPD on patients quality of life.
 - Items are measured on a 0-5 ordered categorical scale for which 0 = never experience this symptom to 5 = experience this symptom continuously

7 Sample Size

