9.2 Derived variables

The primary endpoint consists of several variables: disease-related mortality, endotracheal intubation, vasopressors, renal failure, lung abscess/empyema, pneumonia development and hospital readmission.

The key secondary endpoint is derived from the scores of the diary card with the modified Anthonisen criteria* the patient will fill in on baseline, day 3, day 5, day 10 and day 30. This endpoint will be scored by an independent physician. If there is incomplete resolution of symptoms, this will result in treatment failure. The symptoms are scored as categorical variables and include shortness of breath (slightly or much worse or 'as baseline condition prior to exacerbation'), sputum production (slightly or much more or 'as baseline condition prior to exacerbation'), sputum discoloration (slightly or strongly increased or 'as baseline condition prior to exacerbation') and minor symptoms as coughing, sore throat, fever, wheezing or a blocked or running nose. When one of these symptoms has not been resolved on day 30 this should result in scoring this as treatment failure.

*Example of the diary card with the modified Anthonisen criteria we used to derive our own diary card in Dutch. This original diary card was designed by Jaap Trappenburg et al. and used in a trial that was published in 2011 [15](Thorax 2011;66:977e984):

After evening diner

Compared with previous weeks ...	DAY 1 _/_/2009	DAY 1 _/_/2009	DAY 1 _/_/2009
I am more short of breath than normal	 No  Yes, slightly increased  Yes, clearly increased	 No  Yes, slightly increased  Yes, clearly increased	 No  Yes, slightly increased  Yes, clearly increased
I produce more sputum than normal	 No  Yes, slightly increased  Yes, clearly increased	 No  Yes, slightly increased  Yes, clearly increased	 No  Yes, slightly increased  Yes, clearly increased

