10.2.2 Analyses of Secondary Endpoints

- Treatment failure defined as an incomplete resolution of the clinical signs and symptoms associated with the AECOPD at day 30 after inclusion of the study (i.e not reaching the baseline condition prior to the AECOPD) scored using the modified Anthonisen criteria.
 - Dichotomous variable (yes/no)
 - Description: Number and percentage
 - Test: logistic mixed-effects model
- Change in quality of life using the COPD assessment test
 - Measurements are continuous and paired (multiple (3) measurements in all patients (day 1, 10 and 30))
 - Description:
 - Normal distribution: mean score \pm SD
 - Skewed distribution: median (IQR)
 - Test:
 - mixed effects model with random effects for center and patient to account for the extra hierarchical level in the data. In case of violations of the normality assumptions, transformations of the dependent variable will be applied or the bootstrapping procedure will be used to obtain robust confidence intervals.
 - MCID = a decrease of 2 points after treatment is considered a minimal clinically important difference. When the difference in improvement of the CAT is < 2 points, then this will be considered a clinically non-significant difference[16,17].

- EXACT – Respiratory symptoms scale
 - Measurements are continuous and paired (multiple (3) measurements in all patients (day 1, 10 and 30))
 - Description:
 - Normal distribution: mean score \pm SD
 - Skewed distribution: median (IQR)
 - Test:
 - mixed effects model with random effects for center and patient to account for the extra hierarchical level in the data. In case of violations of the normality assumptions, transformations of the dependent variable will be applied or the bootstrapping will be used to obtain robust confidence intervals.
 - MCID: symptomatic improvement is defined by a decrease of the RS-total score of at least 2 points. When the difference in improvement of the EXACT is < 2 points, then this will be considered a clinically non-significant difference[18].

- Time to complete resolution of symptoms in days according to daily symptom diaries evaluating the modified Anthonisen criteria
 - Continuous variable, unpaired
 - Description:
 - Normal distribution: mean score \pm SD
 - Skewed distribution: median (IQR)
 - Test: mixed-effects model

- Decision to start antibiotic treatment after an initial opposite decision (after 48 hours)
 - Dichotomous variable (yes/no)
 - Description: Number and percentage

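### Time to complete resolution is defined from daily diaries and analysed in days, but the card is scheduled on only five days, so recovery after day 10 is known only to a 20-day interval

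*SAP*

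**What the plan says.** The endpoint is listed in Protocol 8.1.2 as "Time to complete resolution of symptoms according to daily symptom diaries evaluating the modified Anthonisen criteria". Protocol 10.2 and SAP 5.2 carry the same definition. SAP 10.2.2 adds the unit: "Time to complete resolution of symptoms in days according to daily symptom diaries evaluating the modified Anthonisen criteria". It classifies the variable as "Continuous variable, unpaired", summarises it by mean or median, and tests it with a mixed-effects model.

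The collection plan differs:

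- The protocol schedule (8.3) marks the diary row on days 1, 3, 5, 10 and 30. Its footnote reads "This symptom card will be evaluated on the given days by the patient".
- The SAP schedule (6.4) marks its row "Diary cards according to modified" Anthonisen criteria at baseline and days 3, 5, 10 and 30.
- SAP 9.2 describes a card that "the patient will fill in on baseline, day 3, day 5, day 10 and day 30". That sentence introduces the key secondary endpoint (status at day 30), but it describes the same card.

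Protocol 8.3 also says "Patients diary cards will be reviewed at each visit for symptoms and exacerbations", and Protocol 13.1 says much the same. That wording would fit a diary kept between visits.

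**The concern.** A time in days needs a record fine enough to place the event on a day. With cards on days 1, 3, 5, 10 and 30, a patient who recovers on day 11 first shows it on day 30. If that card day is entered as the resolution day, the time is 19 days too long, and the SAP has no rule that says otherwise. It gives no derivation of the resolution day, no treatment of the interval between cards, and no rule for patients unresolved at day 30.

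What is at stake is one of the other secondary endpoints. Its reported times would partly reflect the visit calendar rather than recovery. A temporary resolution, or a relapse that has cleared by day 30, would leave no trace on the cards.

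**Working it through.** The plan states no expected resolution rate, power or event count for this endpoint, so there is no figure of its own to reproduce.

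**Step 1: the grid.** The card days in both schedules are 1, 3, 5, 10 and 30. The gaps are 3 − 1 = 2, 5 − 3 = 2, 10 − 5 = 5 and 30 − 10 = 20 days. Days 11 to 29, 19 consecutive days, have no card.

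**Step 2: an illustrative model (assumption).** Take exponential time to sustained resolution with median m. The proportion unresolved at day t is S(t) = 2^(−t/m), and the proportion resolved is F(t) = 1 − S(t). The medians of 9 to 25 days are assumed. Each patient is dated to the first card on or after the true time. Patients unresolved at day 30 are coded as 30, also an assumption because the SAP gives no rule.

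- Share resolving between days 10 and 30: F(30) − F(10).
- Recorded median: the first card day with F ≥ 0.5.
- Recorded mean: 1 + 2·S(1) + 2·S(3) + 5·S(5) + 20·S(10).
- True mean restricted to 30 days: (m / ln 2)·(1 − S(30)).

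For m = 9: the recorded mean is 1 + 2(0.926) + 2(0.794) + 5(0.680) + 20(0.463) = 17.1. The true restricted mean is 12.98 × 0.901 = 11.7.

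| Assumed median | F(10) | F(30) | Resolve in days 10–30 | Recorded median | Recorded mean | True restricted mean | Excess |
|---|---|---|---|---|---|---|---|
| 9 | 0.537 | 0.901 | 36% | 10 | 17.1 | 11.7 | 5.4 |
| 11 | 0.467 | 0.849 | 38% | 30 | 18.8 | 13.5 | 5.4 |
| 12 | 0.439 | 0.823 | 38% | 30 | 19.5 | 14.3 | 5.3 |
| 25 | 0.242 | 0.565 | 32% | 30 | 24.3 | 20.4 | 3.9 |

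**Step 3: sensitivity.** A simulation with resolution starting after day 1 and medians of 5 to 20 days gives 27% to 40% resolving in days 11 to 30. Those patients are dated late by 10.7 to 13.6 days on average.

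**Step 4: the comparison between arms.** Median and mean behave differently:

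- Medians of 9 and 11: recorded medians are 10 and 30. Recorded means differ by 18.8 − 17.1 = 1.7 days, against a true restricted difference of 13.5 − 11.7 = 1.8.
- Medians of 12 and 25: recorded medians are both 30. Recorded means differ by 24.3 − 19.5 = 4.8 days, against 20.4 − 14.3 = 6.1.

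**The case against.** **This may be a wording conflict, not a data-collection flaw.** The endpoint is called daily in both documents, and review at each visit fits a diary kept at home. That is fair: the documents do not show which was intended. But the protocol footnote and SAP 9.2 describe when the patient completes the card, not when staff look at it, so one side must be corrected. SAP Figure 2 does not settle it. It shows an earlier trial's card with a column per day, introduced as "Example of the diary card with the modified Anthonisen criteria we used to derive our own diary card in Dutch", and the trial's own card is not shown.

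**A reader might infer that everything between days 10 and 30 is missed.** It is not. Resolution lasting to day 30 is seen then and is only undated.

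**A reader might infer that re-exacerbations are under-recorded.** The documents do not make the diary the only source. Clinical assessment, antibiotic and prednisolone consumption, adverse events recorded to day 30 and the day-30 resource-use questionnaire also cover the window.

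**A reader might infer that a 2-day difference would be reported as 20 days, or that a 13-day difference would vanish.** That is true only of the descriptive median in the chosen pairs (9 v 11 and 12 v 25). The planned test compares means, where the first difference is nearly unchanged and the second is attenuated.

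**Recorded days are nominal.** The SAP 6.4 windows are days 9–11 and 28–32, so actual dates would spread slightly. The 20-day gap remains in substance.

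**Conclusion.** The contradiction is real and appears in both documents. As scheduled, the endpoint cannot be derived as a day count: resolution is known only to an interval, at most 20 days wide. Analysing card days as continuous days lengthens the reported times. Under the exponential assumption with medians of 9 to 25 days and unresolved patients coded as 30, the excess is about 4 to 5 days (3.9 to 5.4), and 32% to 38% of patients are dated to day 30 although they resolved in the preceding gap. These sizes rest on assumed medians and an assumed coding rule; the gap itself does not. The effect on the comparison between arms is smaller than on the reported times, and the documents do not support a claim that it is grossly distorted. The primary endpoint and the sample size are unaffected. The point should be corrected, and soon if daily entries are wanted, because days not recorded cannot be recovered after follow-up.

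**What to change.** Reconcile Protocol 8.1.2, 8.3 and 10.2 with SAP 5.2, 6.4, 9.2 and 10.2.2 in one of two ways.

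- **(a) Keep the five cards.** Delete the word daily. Replace the continuous mixed-effects analysis with an interval-censored time-to-event analysis, right-censored at day 30. Alternatively, report the proportion resolved at days 3, 5, 10 and 30 by arm. The analysis change needs SAP wording only; deleting the word from the protocol's endpoint text is a small edit. The price is coarse information after day 10.
- **(b) Collect daily.** If that is intended, correct Protocol 8.3, both schedules and SAP 9.2 to say that the patient completes the card every day to day 30. Use the interval-censored analysis for patients who completed only the five cards. No extra visit is needed, but entry rises from at most 5 × 693 = 3,465 to at most 30 × 693 = 20,790 patient-days, some days will be missing, and a change during enrolment mixes two measurement methods.

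Under either option, state in SAP 9.2 how the resolution day is derived, whether resolution must be sustained, and how death and non-resolution by day 30 are handled.

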9.3 Protocol Deviations

When a physician decides to prescribe antibiotic therapy even though the patient has a low serum concentration of procalcitonin ($\leq 0.25 \mu\text{g/mL}$) this leads to a protocol violation. The patient might recover because of the antibiotic therapy instead of still experiencing symptoms on day 30, which could directly impact the primary endpoint. This subject should not be analyzed in the per protocol analysis, because of this major protocol deviation/violation.

Early termination of antibiotic therapy, in both groups, could have an impact on the primary endpoint. This could happen when a patient has an initial quick recovery and gets discharged from the hospital without antibiotic therapy and then has a relapse. We do not expect this to happen more in one of the two treatment arms, although a high PCT might lead to less frequent discontinuation of the treatment when the patient is discharged in the first 5 days (the antibiotic therapy should be given during 5 days in both groups).

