### **Statistical and analytical plans**

#### **Primary analysis**

The primary endpoint is defined as 30-day treatment failure. The per protocol (PP) population is the main analysis population. An analysis will be performed for the randomly

---

allocated antibiotic strategy (i.e. usual care versus antibiotics in patients with PCT >0.25 µg/L). The difference and corresponding 95% confidence interval (two-sided) in the incidence of the primary endpoint between the randomly allocated strategies (biomarker-guided drug use minus drug-in-all) will be determined. Non-inferiority will be concluded if the upper limit of the 95% confidence interval does not exceed the prespecified non-inferiority margin of 5%.

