6.1 General Study Design and Plan

- Study design: prospective, randomized-controlled trial. Patients will be randomized to biomarker-guided treatment (based on blood procalcitonin level) or to usual care. In the usual care arm, and in the biomarker guided-arm in case of high ($> 0.25\mu\text{g/L}$) procalcitonin, patients will receive amoxicillin-clavulanic acid.
- Type of Comparison: non-inferiority.
- Type of control(s): usual care
- Level and method of blinding (e.g. double-blind): The patient and the outcome assessor will be blinded for the allocated treatment strategy. Two independent physicians will be selected per center to be the outcome assessors. The patient will not be blinded for the treatment itself (prednisolone with or without antibiotic therapy).
- Method of treatment assignment: We will use a block-randomisation with randomly alternating blocks of 4 and 6 patients (random permuted block randomisation). The randomisation will be stratified per center.
- At what point in time subjects are randomized relative to treatments, events and study periods: Upon presentation at the emergency department, patients will be clinically

judged for in- and exclusion criteria, among which indication for hospitalization. When eligible the patient will be notified about the study. When the patient is interested in participating, the patient information form will be discussed by the treating physician. The participation being voluntarily and the opportunity to discontinue participation will be made clear by the treating physician. Informed consent will be requested with at least two hours of time to decide

- Sequence and duration of all study periods: screening will occur on the first day of admission as described above, baseline characteristics will be collected within 24 hours of admission, active treatment will be 5 days, follow-up will be 30 days.

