In international literature there is scarce information about the percentages of treatment failure in patients admitted with an AECOPD receiving usual care. Therefore, we have performed a further search on PCT studies with a primary outcome of 30-day treatment failure. In the study by Schuetz et al. [6], who studied patients with lower respiratory tract infection, 30-day treatment failure was observed in 15.5% of the patients randomised to biomarker-based treatment, as compared to 18.9% in those randomised to usual care. This implies a relative risk of 0.82 in favour of the biomarker-based strategy. The study by Schuetz et al. was designed as a non-inferiority study, using a non-inferiority boundary of 7.5%. In view of these data we decided to design our study as a non-inferior study, whereas we choose a non-inferiority boundary of 5.0%. We based the primary outcome on the study of Huang et al. [13]. The incidence of the primary outcome was 20.4%. Using the relative risk of 0.82 in favour of the PCT-guided treatment group we expect the incidence of the primary outcome to be 16.7% in the PCT-guided treatment group. Then a total sample size of 626 is required (313 per treatment arm) to demonstrate non-inferiority with a power of 80%, and applying a one-sided alpha error of 0.025. We aim to enroll a total of 690 patients, accounting for a 10% drop-out rate.

8 General Analysis Considerations

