8.2.2 Per Protocol Population

- All subjects who:
 - met all inclusion/exclusion criteria,
 - attained a sufficient compliance to the treatment received, treatment with prednisolone and/or antibiotics, when prescribed on admission for at least 5 days,
 - did not present serious deviations from the protocol.

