8.2.3 Safety Population

- All subjects who received any study treatment (including control) but excluding subjects who drop out prior to receiving any treatment.

The analysis of all the efficacy variables will be performed on both the ITT and the PP populations in order to assess the robustness of the findings from the ITT population.

All the demographic and baseline patients' characteristics and safety outcomes will be analysed using the ITT population.

All efficacy variables will be analysed for ITT and the PPS, and the PP population will be considered the primary population for assessing efficacy.

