11.5 Clinical Laboratory Evaluations

The summary statistics will be produced in accordance with section 9.

We do not expect difficulties in differences between centers in normal ranges of the most important laboratory evaluations. The PCT concentration has a fixed cut-off, determined by the initiators of the trial. CRP concentration will be reported with a mean value with standard deviations, the normal ranges do not interfere with the type of reporting of this value.

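### SAP 9.3 gives the PCT cut-off for per-protocol exclusion in µg/mL instead of µg/L and names no arm, so as written it excludes patients treated as the protocol allows

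*SAP*

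**What the plan says.** SAP 9.3 describes one specific deviation: a physician prescribes antibiotics despite "a low serum concentration of procalcitonin ($\leq 0.25 \mu\text{g/mL}$) this leads to a protocol violation". It then states the consequence: "This subject should not be analyzed in the per protocol analysis, because of this major protocol deviation/violation".

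This feeds into SAP 8.2.2, which limits the per-protocol (PP) set to patients who, besides meeting the eligibility and compliance conditions, "did not present serious deviations from the protocol". The text under SAP 8.2.3 says that "the PP population will be considered the primary population for assessing efficacy". Protocol section 10 and SAP 10 say the same.

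The treatment rule is given in a different unit. SAP 6.1 assigns amoxicillin-clavulanic acid "in the biomarker guided-arm in case of high ($> 0.25\mu\text{g/L}$) procalcitonin". The primary analysis text in Protocol section 10 describes the comparison as "usual care versus antibiotics in patients with PCT >0.25 µg/L". SAP 11.5 adds: "The PCT concentration has a fixed cut-off, determined by the initiators of the trial".

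**The concern.** A deviation rule should be the mirror image of the treatment rule it polices. Here the treatment rule turns on 0.25 µg/L and the deviation rule on 0.25 µg/mL. Between the two values lies a wide band of patients for whom the algorithm directs antibiotics and SAP 9.3 calls the same antibiotics a major violation.

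The sentence also does not say to which arm it applies. Usual-care physicians are free to prescribe antibiotics whatever the PCT value, which they do not see. PCT is nevertheless measured in that arm and will be in the data once the study is complete, so a program could apply the rule there too.

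At stake is who enters the confirmatory non-inferiority comparison, because PP is the primary population. Removing patients according to treatment received and PCT level breaks the randomised comparison, and the direction of the resulting bias cannot be predicted from the documents.

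**Working it through.** **1. The cut-off wherever it is stated**

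| Place | Cut-off | In µg/L |
|---|---|---|
| Protocol 1 (also given there as 0.25 ng/mL) | 0.25 µg/L | 0.25 |
| Protocol 3, treatment table | 0.25 µg/L | 0.25 |
| Protocol 10, primary analysis | 0.25 µg/L | 0.25 |
| SAP 6.1 | 0.25 µg/L | 0.25 |
| SAP 9.3 | 0.25 µg/mL | 0.25 × 1000 = 250 |

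The ng/mL form agrees: 0.25 ng/mL × 1000 mL/L ÷ 1000 ng/µg = 0.25 µg/L. SAP 9.3 is the only outlier, by a factor of 250 / 0.25 = 1000. No section introduces a second threshold.

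**2. Antibiotic-treated patients that SAP 9.3 would flag**

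| Patient given antibiotics | Allowed by protocol? | Flagged as written? | Flagged with µg/L only? | Flagged with µg/L and arm limit? |
|---|---|---|---|---|
| PCT arm, ≤ 0.25 µg/L | no | yes | yes | yes |
| PCT arm, > 0.25 to 250 µg/L | yes | yes | no | no |
| Usual care, ≤ 0.25 µg/L | yes | yes | yes | no |
| Usual care, > 0.25 to 250 µg/L | yes | yes | no | no |

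Only the last column matches the protocol. Correcting the unit alone leaves the third row wrong.

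**3. Baseline for a sense of size**

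Inputs from SAP 7 and 8.5.5: failure rates 20.4% (usual care) and 16.7% (PCT-guided), margin 5 points, power 80%, one-sided alpha 0.025, final two-sided alpha 0.0492, and 315 per arm.

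n per arm = [pC(1−pC) + pT(1−pT)] × (zα + zβ)² / (margin − (pT − pC))²

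= (0.204 × 0.796 + 0.167 × 0.833) × (1.960 + 0.842)² / 0.087² = 312.6, so 313, as the plan states. At alpha 0.0492 the result is 314.2, so 315, again as stated. Power with 315 per arm at alpha 0.0492 is 80.1%.

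**4. Illustration for the PCT arm**

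Assumptions: a share h of the PCT arm lies above 0.25 µg/L, none exceeds 250 µg/L, all are treated per algorithm, and event rates stay as planned. The usual-care arm is kept at 315 here to isolate the unit error.

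Power = Φ(0.087 / √[pC(1−pC)/315 + pT(1−pT)/nT] − z), with z taken at two-sided alpha 0.0492.

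| h | Removed from 315 | Left (nT) | Power |
|---|---|---|---|
| 5% | 16 | 299 | 79.1% |
| 10% | 31 | 284 | 78.1% |
| 20% | 63 | 252 | 75.7% |
| 40% | 126 | 189 | 68.9% |

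**5. Illustration with the rule read literally in both arms**

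Protocol 1 reports that 65% of patients hospitalised for COPD in the Netherlands receive antibiotics. If that share held in the usual-care arm (assumption), with no value above 250 µg/L, 315 × 0.35 ≈ 110 usual-care patients would remain. Power would then be 50.3% at h = 5% and 45.3% at h = 40%.

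The power figures in steps 4 and 5 count lost patients only. They do not include selection bias.

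**The case against.** The strongest reply is that the documents resolve the slip themselves. SAP 9.3 speaks of violating the protocol, and the protocol sets the boundary at 0.25 µg/L. SAP 6.1 repeats that value, and SAP 11.5 calls the cut-off fixed. A treated PCT-arm patient with, say, 0.6 µg/L followed the protocol. A flag that removed nearly every treated patient would be noticed when programmed. An intention-to-treat analysis of all efficacy variables is also planned.

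The intended arm can be inferred in the same way. Prescribing despite a low value implies that the physician knows the value, which holds only in the PCT arm.

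Most of this stands. The intended rule can be reconstructed, and literal application is not the likely outcome. What does not follow is that the text may stay. A SAP exists so that the primary population can be derived without guessing intent. An analyst who silently corrects this sentence has departed from the plan on the population that decides the trial.

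Three stronger readings are tempting and are not supported:

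- **One-sided loss.** A reader might infer that only the PCT arm loses patients, leaving an untreated low-PCT group against an intact usual-care arm. That takes the unit literally but supplies the arm from intent. Read literally throughout, the rule reaches both arms.
- **Sole exclusion rule.** A reader might take SAP 9.3 as the only explicit PP exclusion. SAP 8.2.2 and Protocol section 10 also exclude for failed eligibility and insufficient compliance. SAP 9.3 is the only place that names this particular event and orders removal for it.
- **Deliberate second threshold.** Nothing in either document suggests one.

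**Conclusion.** Wrong as written. The factor of 1000 is certain and needs no assumption. So is the absence of an arm restriction in a sentence about a value measured in both arms. Together they make SAP 9.3 contradict the treatment rules in Protocol sections 3 and 5 and in SAP 6.1, within the definition of the primary analysis population.

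The unit is probably a slip, and harm to the result arises only if the sentence is applied literally. How many patients that would affect cannot be derived from the documents. The 16 to 126 of 315 PCT-arm patients, and the matching fall in power from 80.1% to between 79.1% and 68.9%, rest on an assumed 5% to 40% above 0.25 µg/L, all treated. The lower power with both arms affected rests in addition on carrying the national 65% antibiotic share into the trial. None of these figures forecasts what will happen.

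**What to change.** In SAP 9.3:

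1. State the cut-off in µg/L, so that the deviation rule is the exact complement of the treatment rule in Protocol sections 3 and 10 and SAP 6.1.
2. State that this deviation applies only to patients randomised to PCT-guided care.
3. Specify that the PP flag is programmed from the laboratory PCT value in µg/L together with the randomised arm, and check the unit of the exported laboratory field before the flag is run.

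The cost is one unit and one clause in the SAP, made before database lock. It needs no new data, and treatment and sample size do not change.
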